10.4 Primary objective

The primary objective is to demonstrate the antitumor activity of LDK378 in patients with ALK-positive non-small cell lung cancer (NSCLC) previously treated with alectinib.

10.4.1 Variable

The primary variable is the overall response rate (ORR), which is defined as the proportion of patients with a best overall confirmed response of CR or PR, as assessed per RECIST 1.1 ([Appendix 2](#)) by the investigator.

10.4.2 Statistical hypothesis, model, and method of analysis

The primary analysis will be performed on the FAS. The primary efficacy endpoint ORR will be estimated and reported along with the exact (Clopper-Pearson) 95% confidence interval (CI). No statistical hypothesis testing is planned.

10.4.3 Handling of missing values/censoring/discontinuations

Confirmed partial or complete responses reported prior to any additional anticancer therapy will be considered as responses in the calculation of ORR, irrespective of the number of missed assessments before response.

Patients with a best overall response of “Unknown” per RECIST 1.1 will be considered as non-responders in estimating the ORR.

Patients who have disease progression and continue to receive the study treatment after progression will qualify for progressive disease at the time of first documented progression. Tumor assessments performed after the first documented progression will not be considered for ORR. This will apply to secondary efficacy endpoints as well.

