15.1.17 Best overall response

The best overall response is the best response recorded from the start of the treatment until disease progression/recurrence (taking as reference for PD the smallest measurements recorded since the treatment started). In general, the patient's best response assignment will depend on the achievement of both measurement and confirmation criteria.

The best overall response will usually be determined from response assessments undertaken while on treatment. However, if any assessments occur after treatment withdrawal the protocol should specifically describe if these will be included in the determination of best overall response and/or whether these additional assessments will be required for sensitivity or supportive analyses. As a default, any assessments taken more than 30 days after the last dose of study treatment will not be included in the best overall response derivation. If any alternative cancer therapy is taken while on study any subsequent assessments would ordinarily be excluded from the best overall response determination. If response assessments taken after withdrawal from study treatment and/or alternative therapy are to be included in the main endpoint determination, then this should be described and justified in the protocol.

Where a study requires confirmation of response (PR or CR), changes in tumor measurements must be confirmed by repeat assessments that should be performed not less than 4 weeks after the criteria for response are first met.

Longer intervals may also be appropriate. However, this must be clearly stated in the protocol. The main goal of confirmation of objective response is to avoid overestimating the response rate observed. In cases where confirmation of response is not feasible, it should be made clear when reporting the outcome of such studies that the responses are not confirmed.

- -For non-randomized trials where response is the primary endpoint, confirmation is needed.
- -For trials intended to support accelerated approval, confirmation is needed
- For all other trials, confirmation of response may be considered optional.

The best overall response for each patient is determined from the sequence of overall (lesion) responses according to the following rules:

- CR = at least two determinations of CR at least 4 weeks apart before progression where confirmation required or one determination of CR prior to progression where confirmation not required

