2.7.3 Handling of missing values/censoring/discontinuations

Confirmed PR or CR reported prior to any additional anticancer therapy will be considered as responses in the calculation of ORR, irrespective of the number of missed assessments before response.

Patients with a best overall response of 'Unknown' per RECIST 1.1 will be considered as non-responders in estimating the ORR.

Patients who have disease progression and continue to receive the study treatment after progression will qualify for PD at the time of first documented progression. Tumor assessments performed after the first documented progression will not be considered for ORR. This will apply to secondary efficacy endpoints as well.

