2.8 Analysis of secondary variables

2.8.1 Efficacy

The key secondary and other secondary efficacy endpoints are provided in [Table 1-1](#). All tumor response related endpoints under the secondary efficacy objectives (DCR, TTR, DOR, PFS, and OIRR), as well as the primary efficacy endpoint ORR, will be analyzed based on the investigator assessments as per RECIST 1.1. Confirmation of response is required for all response endpoints, as per RECIST 1.1.

The definitions and details on the derivation of the efficacy endpoints are given in Section 15 (Appendix 2) of the CLDK378A1201 protocol. Further details and rules needed for programmatic implementation of RECIST 1.1 guidelines are provided in [Section 4.7.1](#).

All secondary efficacy endpoint analyses will be performed based on the FAS, unless otherwise specified. All efficacy data, such as tumor assessments and respective efficacy endpoints, will be listed by patient.

Best overall response and DCR will be summarized by subgroup (as defined in [Section 2.1](#)) as well as the primary efficacy endpoint ORR.

Best overall response

Best overall response (BOR) will be assessed based on reported lesion responses at different evaluation time points. Both CR and PR must be confirmed by repeat assessments performed not less than 4 weeks after the criteria for response are first met. The next scheduled assessment may be used for purposes of confirmation of response. If there is only one confirmatory assessment available which has been performed earlier, the status PR or CR will not be assigned. Unconfirmed PR and unconfirmed CR are considered as SD if >6 weeks after start of study drug, otherwise considered as UNK. BOR for each patient is determined from the sequence of overall (lesion) responses according to the following rules:

- CR = at least two determinations of CR at least 4 weeks apart before progression.
- PR = at least two determinations of PR or better at least 4 weeks apart before progression (and not qualifying for a CR).
- SD = at least one SD assessment (or better) >6 weeks after start of study drug (and not qualifying for CR or PR).
- PD = progression ≤12 weeks after start of study drug (and not qualifying for CR, PR or SD).
- UNK = all other cases (i.e., not qualifying for confirmed CR or PR and without SD after more than 6 weeks or progression within the first 12 weeks)

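### Does the plan leave open whether scans more than 30 days after the last dose count toward the primary response rate?

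*Protocol*

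**What the plan says.** Protocol 10.4.1 defines ORR as the proportion of patients with confirmed CR or PR by investigator assessment under RECIST 1.1, and refers to Appendix 2 for the criteria. Protocol 10.4.3 says which responses count: "Confirmed partial or complete responses reported prior to any additional anticancer therapy will be considered as responses in the calculation of ORR", however many scans were missed beforehand. Scans after first documented progression are set aside. SAP 2.7.3 repeats this: "Confirmed PR or CR reported prior to any additional anticancer therapy will be considered as responses in the calculation of ORR".

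Appendix 2 is the sponsor's general guideline for solid-tumour studies. Its section 15.1.17 gives this rule, to hold unless a study says otherwise: "any assessments taken more than 30 days after the last dose of study treatment will not be included in the best overall response derivation". On scans after treatment withdrawal it says that "the protocol should specifically describe if these will be included in the determination of best overall response", and that if they "are to be included in the main endpoint determination, then this should be described and justified in the protocol".

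SAP 2.8.1 refers back to that guideline: "The definitions and details on the derivation of the efficacy endpoints are given in Section 15 (Appendix 2) of the CLDK378A1201 protocol". The same section also writes out a study-specific derivation of best overall response (BOR). It requires confirmation at least 4 weeks later and excludes scans after further antineoplastic therapy. It also states: "Unconfirmed PR and unconfirmed CR are considered as SD if >6 weeks after start of study drug, otherwise considered as UNK".

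**The concern.** Two limits appear in Appendix 2: one for new therapy and one for time since last dose. The protocol body and the SAP restate the first and never mention the second, while both point to Appendix 2 for definitions. SAP section 3 declares no changes to the protocol's analyses. A programmer who works from Appendix 2 could apply the 30-day limit, and one who works from the SAP would not.

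The scans in question will exist. Protocol 4.1, 6.1.3 and 7.1.5.2 keep patients who stop without progression on the 8-weekly schedule until progression. Confirmation needs two scans, so losing the second turns a responder into stable disease. The sets for time to response and duration of response follow the responder count. The disease control rate can change for patients who stop very early. In an open-label, single-arm trial of about 20 patients with no independent review, the rule for which scans count should be fixed in advance.

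**Working it through.** **Inputs.** Cycles of 28 days (Protocol 6.1.4); scans every 8 weeks from Cycle 3 Day 1, window ±7 days (7.2.1.2); confirmation at least 4 weeks later (SAP 2.8.1); N = 20, benchmark 10%, at least 6 responders needed for the exact 95% interval to exclude 10% (Protocol 10.8).

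**The plan's own figures.** P(X ≥ 6) for X ~ Bin(20, p) is 0.5836, 0.7546 and 0.8744 at p = 0.30, 0.35 and 0.40, against the stated 58.4%, 75.5% and 87.4%. The Clopper-Pearson interval for 6/20 is 11.89% to 54.28%, as stated.

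**When the two rules differ.** Planned scans fall on Day 1 + 56 = 57, then 113 and 169. With last dose on day L, the Appendix 2 default keeps a scan on day s if s − L ≤ 30.
- Day 57 kept: L ≥ 27. Day 113 dropped: L ≤ 82. That is Days 27 to 82, or 56 days.
- For a first response on Day 113 confirmed on Day 169, the range is Days 83 to 138, again 56 days.
- With scans on Days 64 and 106 the first range narrows to Days 34 to 75 (42 days). With scans on Days 50 and 120 it widens to Days 20 to 89 (70 days).
- With L ≤ 26 the Day 57 scan is dropped too and BOR becomes unknown.
- If an end-of-treatment scan is taken within 7 days of last dose, it can confirm a Day 57 PR only from Day 57 + 28 = 85, so L ≥ 78. That covers Days 78 to 82 and leaves 51 of the 56 days.

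These are ranges of dates, not probabilities. For L on Days 27 to 56 (30 of the 56 days), the first PR is itself recorded after the drug has stopped. At L = 27 the patient must hold the response, without progression or new therapy, until 113 − 27 = 86 days off drug.

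**Effect on the result.** One patient is 1/20 = 5 points. The interval for 5/20 is 8.66% to 49.10%, which includes 10%. If exactly one responder is reclassified, the reading against 10% flips only when the other 19 patients include exactly 5 responders: C(19,5) p^5 (1 − p)^14 = 0.1916, 0.1468 and 0.0933 at p = 0.30, 0.35 and 0.40. Assume the chance of one such reclassification is 10% to 30% (the documents give no figure). The overall chance of a flip then runs from 0.10 × 0.0933 = 0.9% to 0.30 × 0.1916 = 5.7%.

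**Which rule the study text gives.**
- SAP 2.7.3 excludes scans after progression, and SAP 2.8.1 excludes scans after further therapy. Neither uses the date of last dose.
- SAP 4.7.1, on implementing RECIST, again names only additional anticancer therapy for ORR.
- The reasons for an unknown BOR listed in SAP 2.8.1 include new therapy before the first scan, but none for a scan too long after last dose.
- SAP 2.8.2 does write a 30-day limit after last dose where one is wanted, for the safety tables.
- Protocol 4.1.2.1 has tumour response evaluated every 8 weeks until progression, withdrawal of consent, loss to follow-up or death, not until the last dose. Table 7-2 gives one imaging schedule for treatment and follow-up together.

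**The case for a change.** The strongest contrary reading is that repeating one Appendix 2 limit does not cancel the other. The sentence in 10.4.3 is about missed scans, not time off drug, and could be taken as acting only on responses already derived under Appendix 2. Scanning to progression does not settle it either, because Appendix 2 treats such follow-up as usual and still sets its BOR default. The case can also arise in practice. Under Protocol 6.3 a hold of more than 28 days generally ends treatment, and by then almost all of the 30 days has gone.

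Part of this stands. The override is nowhere stated, and the request in Appendix 2 that inclusion of late scans be described and justified is not met in so many words. It does not follow that two algorithms are equally live. Appendix 2 is a generic text and calls its limit a default. The SAP supplies the study's own derivation, and SAP 4.7 offers its text as the more detailed rules for programming. SAP section 3 is not evidence of conflict, because SAP 2.7.3 matches Protocol 10.4.3.

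**Conclusion.** No change to the plan is needed. The SAP's derivation can be programmed as written and gives one ORR: confirmed responses before progression and before new anticancer therapy, whatever the time since last dose. That is a sound rule here, because scheduled scanning continues to progression and new therapy already closes the window. What is missing is a cross-reference saying that the generic default does not apply; supplying it would leave the main analysis unchanged.

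An extra ORR under the 30-day limit would gain little. It would test a rule the study does not appear to intend, for a group that is probably well under one patient in 20. BOR and all tumour assessments are listed by patient (SAP 2.7.4 and 2.8.1), so any such patient would be visible. No hypothesis test is planned.

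The conclusion rests on two assumptions: that the SAP's specific text governs over the appendix default, and that few patients both stop early and keep an untreated response to the next scan. If one patient did fall in the gap, the estimate would differ by 5 points between the two readings.

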10.4.4 Supportive analyses

The best overall response will be listed by patient and summarized along with the ORR.

10.5 Secondary objectives

All secondary efficacy analyses will be performed on the FAS, unless otherwise specified.

10.5.1 Key secondary objective(s)

Disease control rate

Disease control rate (DCR) is defined as the proportion of patients with a best overall response of CR, PR or SD, as assessed per RECIST 1.1 by the investigator. DCR will be estimated and reported along with the exact 95% CI.

Duration of response

Among patients with a confirmed response (PR or CR) per RECIST 1.1 by the investigator, the duration of response (DOR) is defined as the time from first documented response (PR or CR) to the date of first documented disease progression or death due to any cause. DOR will be listed by patient and will be described using Kaplan-Meier methods and relevant summary statistics such as median DOR and the 95% CI. Censoring rules for DOR follow those for PFS.

Time to response

Among patients with a confirmed response (PR or CR) per RECIST 1.1 by the investigator, the time to response (TTR) is defined as the time from the date of the first dose of LDK378 to first documented response (PR or CR). TTR will be listed by patient and will be summarized using descriptive statistics for patients with a confirmed response.

10.5.2 Other secondary efficacy objectives

Progression-free survival

Progression-free survival (PFS) is defined as the time from the date of first dose of LDK378 to the date of first documented disease progression per RECIST 1.1 or death due to any cause. A patient who has not progressed or died at the date of the analysis or when he/she receives any further anticancer therapy in the absence of disease progression will be censored at the time of the last adequate tumor evaluation before the earlier of the cut-off date or the anticancer therapy date. By default, if disease progression or death for any reason is documented after one single missing tumor evaluation, the actual event date of disease progression/death will be used for the PFS event date. If disease progression or death for any reason is documented after two or more missing tumor evaluations, the PFS time of these patients will be censored at the date of the last adequate tumor evaluation without PD. Censoring rules will be detailed in the RAP. PFS will be listed by patient and will be described using Kaplan-Meier methods and relevant summary statistics such as median PFS and the 95% CI.

Overall survival

Overall survival (OS) is defined as the time from the date of first dose of LDK378 to the date of death due to any cause. OS time for patients who are alive at the end of the study or are lost to follow-up will be censored at the date of last contact. OS will be listed by patient and will be described using Kaplan-Meier methods and relevant summary statistics such as median OS and the 95% CI.

Overall intracranial response rate

Overall intracranial response rate (OIRR) is calculated based on response assessments in the brain for patients having measurable brain metastases at baseline (i.e. at least one target lesion in the brain). OIRR is defined as the ORR based on target, non-target and new lesions in the brain and defined as the proportion of patients with a best overall confirmed response of CR or PR in the brain, as assessed per RECIST 1.1 by the investigator. OIRR will be estimated and reported along with the exact 95% CI. The best overall intracranial response will be listed by patient and will be summarized along with the OIRR. These analyses will be conducted for patients with measurable brain metastases at baseline.

10.5.3 Safety objectives

10.5.3.1 Analysis set and grouping for the analyses

For all safety analyses, the safety set will be used. All listings and tables will be presented for all patients.

The overall observation period will be divided into three mutually exclusive segments:

1. Pre-treatment period: from day of patient's informed consent to the day before first dose of study medication
2. On-treatment period: from day of first dose of study medication to 30 days after last dose of study medication
3. Post-treatment period: starting at day 31 after last dose of study medication.

The safety summary tables will include only data collected during the on-treatment period. However, all safety data will be listed with data collected during the pre-treatment and post-treatment period flagged.

10.5.3.2 Adverse events (AEs)

Summary tables for adverse events (AEs) will include only AEs observed during the on-treatment period. However, all safety data (including those from the pre and post-treatment periods) will be listed and those collected during the pre-treatment and post-treatment period will be flagged.

The incidence of treatment-emergent AEs (new or worsening from baseline) will be summarized by system organ class and/or preferred term, severity (based on CTCAE grades), type of AE, and relation to study treatment. Deaths will also be listed by patient and tabulated.

Specific safety event categories (SEC) will be considered. Such categories consist of one or more well-defined safety events which are similar in nature and for which there is a specific clinical interest in connection with the study treatment. For each specified category, the number and percentage of patients with at least one event per category will be summarized.

10.5.3.3 Laboratory abnormalities

For laboratory tests covered by the CTCAE version 4.03, the study's biostatistical and reporting team will grade laboratory data accordingly. For laboratory tests covered by CTCAE, a Grade 0 will be assigned for all non-missing values not graded as 1 or higher. In the unlikely case when a local laboratory normal range overlaps into the higher (i.e. non-zero) CTC grade, the laboratory value will still be taken as within normal limits and assigned a CTC grade of zero. Grade 5 will not be used.

For laboratory tests where grades are not defined by CTCAE, results will be graded by the low/normal/high classifications based on laboratory normal ranges.

The following summaries will be generated separately for hematology and biochemistry laboratory tests:

- shift tables using CTCAE grades to compare baseline to the worst on-treatment value

- for laboratory tests where CTCAE grades are not defined, shift tables using the low/normal/high/(low and high)

Listing of all laboratory data with values flagged to show the corresponding CTCAE grades and the classifications relative to the laboratory normal ranges will be generated.

A separate listing will display notable laboratory abnormalities (i.e., newly occurring CTCAE grade 3 or 4 laboratory toxicities).

[figure not shown]
[figure not shown]
In addition to the above mentioned tables and listings, other [REDACTED] analyses, for example figures plotting time course of raw or change in laboratory tests over time or box plots might be specified in the RAP.

[figure not shown]
[figure not shown]
10.5.3.4 Other safety data

Data from other tests (including ECGs and vital signs) will be summarized and listed, notable values will be flagged, and any other information collected will be listed as appropriate. Definitions of notably abnormal results will be provided in the RAP.

10.5.3.5 Tolerability

Tolerability will be evaluated in terms of dose reductions or drug interruptions due to an AE.

10.7 Interim analysis

No interim analysis is planned in this study.

10.8 Sample size calculation

The study does not include formal statistical hypothesis testing and the sample size (N=20) is not derived based on power considerations.

A response rate of 10% or less is considered as an insufficient level of activity for the proposed patient population. With a sample size of 20 patients, there is an approximately 58.4% chance that the exact 95% CI will exclude an insufficient response rate of 10% when the true ORR is 30%. The probability increases to 75.5% and 87.4%, when the true ORRs are 35% and 40%, respectively. For an observed response rate of 30.0% (6 responders in 20 patients), the exact 95% CI is (11.9%, 54.3%). The operating characteristics of this study are summarized in [Table 10-1](#).

Table 10-1 Operating characteristics for various ORRs when N=20 patients

True ORR	Probability that exact 95% CI excludes an insufficient level of 10%*	Expected number of responders	Observed ORR and exact 95% CI
30%	58.4%	6	30.0% (11.9%, 54.3%)
35%	75.5%	7	35.0% (15.4%, 59.2%)
40%	87.4%	8	40.0% (19.1%, 63.9%)

*Of 20 patients at least 6 responders are required to meet the criteria (i.e., exact 95% CI excludes an insufficient level of 10%), thus it is calculated as a binomial probability that $\geq 6/20$ responders are observed given the true ORR.

10.9 Power for analysis of key secondary variables

Not applicable

11 Ethical considerations and administrative procedures

11.1 Regulatory and ethical compliance

This clinical study was designed, shall be implemented and reported in accordance with the ICH Harmonized Tripartite Guidelines for Good Clinical Practice, with applicable local regulations (including European Directive 2001/20/EC and US Code of Federal Regulations Title 21), and with the ethical principles laid down in the Declaration of Helsinki.

